5.1.2 Modified Intent-to-Treat (mITT) Populations

Sensitivity analyses of the primary efficacy endpoint, when applicable, will be performed on two modified ITT populations below:

Modified ITT Genotype (mITT-GT) Population

mITT-GT population includes subjects in the ITT population excluding subjects with genotype other than HCV GT2 infection as determined in Section 10.9.

Modified ITT Genotype and Virologic Failure (mITT-GT-VF) Population

mITT-GT-VF includes all subjects in the ITT-GT population defined above, excluding subjects who did not achieve SVR₁₂ for reasons other than virologic failure.

Demographic analyses will also be performed on the mITT population(s), if needed.

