10.0 Efficacy Analysis

10.1 General Considerations

General Considerations

Treatment effects will be evaluated based on a 2-sided significance level of 0.050 (when rounded to three decimal places), and all efficacy analyses will be performed on the ITT population, unless otherwise specified.

Missing data will be imputed as described in Section 6.3 for analyses of the HCV RNA endpoints of SVR.

Plasma HCV RNA levels will be determined for each sample collected by the central laboratory using the Roche COBAS[®] AmpliPrep/COBAS[®] TaqMan[®] HCV Quantitative Test, v2.0. The lower limit of detection (LLOD) and lower limit of quantification (LLOQ) for this assay (regardless of genotype) are both 15 IU/mL.

HCV RNA results that are detectable but not quantifiable are reported as "< 15 IU/ML HCV RNA DETECTED" and those that are undetectable are reported as "HCV RNA NOT DETECTED" in the database.

The notation "HCV RNA < LLOQ" is used to represent all HCV RNA values < 15 IU/mL, including values reported as "HCV RNA NOT DETECTED" or "< 15 IU/ML HCV RNA DETECTED." HCV RNA \geq LLOQ are all quantifiable values.

IL28B rs12979860 will be resulted as C/C, C/T, or T/T by the central laboratory.

Definitions for Efficacy Endpoints

A confirmed quantifiable value during treatment is defined as any two consecutive HCV RNA measurements \geq LLOQ (or 100 IU/mL for **Breakthrough**), either both during treatment or at the final treatment measurement and the next consecutive post-treatment measurement. A confirmed quantifiable post-treatment value is defined as any two consecutive post-treatment HCV RNA measurements \geq LLOQ.

Breakthrough = confirmed HCV RNA \geq 100 IU/mL after HCV RNA $<$ LLOQ during the Treatment Period; or confirmed increase from nadir in HCV RNA (two consecutive HCV RNA measurements $>$ 1 \log_{10} IU/mL above nadir) at any time point during the Treatment Period. A single breakthrough value (\geq 100 IU/mL or $>$ 1 \log_{10} above nadir) followed by lost to follow-up also will be considered a breakthrough (i.e., will not require confirmation).

EOT failure = HCV RNA \geq LLOQ at end of treatment with at least 6 weeks of treatment, where the HCV RNA value must be collected on or after Study Drug Day 36 and study drug duration \geq 36 days.

On-treatment virologic failure = Breakthrough or EOT failure.

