SVR₄ = HCV RNA $<$ LLOQ in the SVR₄ window (4 weeks after the last actual dose of study drug) without any confirmed quantifiable (\geq LLOQ) post-treatment value before or during that SVR window.

SVR₁₂ = HCV RNA $<$ LLOQ in the SVR₁₂ window (12 weeks after the last actual dose of study drug) without any confirmed quantifiable (\geq LLOQ) post-treatment value before or during that SVR window.

SVR₂₄ = HCV RNA $<$ LLOQ in the SVR₂₄ window (24 weeks after the last actual dose of study drug) without any confirmed quantifiable (\geq LLOQ) post-treatment value before or during that SVR window.

Relapse₄ = confirmed HCV RNA \geq LLOQ between end of treatment and 4 weeks after last actual dose of study drug (up to and including the SVR₄ assessment time point) for a subject with HCV RNA $<$ LLOQ at Final Treatment Visit who completed treatment (defined as study drug duration \geq 52 days for Arm A and \geq 77 days for Arm B), excluding reinfection as described below.

Relapse₁₂ = confirmed HCV RNA \geq LLOQ between end of treatment and 12 weeks after last actual dose of study drug (up to and including the SVR₁₂ assessment time point) for a

subject with HCV RNA < LLOQ at Final Treatment Visit who completed treatment (defined as study drug duration ≥ 52 days for Arm A and ≥ 77 days for Arm B), excluding reinfection as described below.

Relapse₂₄ = confirmed HCV RNA \geq LLOQ within the SVR₂₄ window for a subject who achieved SVR₁₂ and has HCV RNA data available in the SVR₂₄ window, excluding reinfection.

Relapse_{overall} = confirmed HCV RNA \geq LLOQ between end of treatment and up to and including the last HCV RNA measurement collected in the PT Period for a subject with HCV RNA < LLOQ at Final Treatment Visit who completed treatment (defined as study drug duration ≥ 52 days for Arm A and ≥ 77 days for Arm B), excluding reinfection.

Only subjects who have at least one post-treatment HCV RNA value will be included in analyses of relapse. For the analysis of relapse, completion of treatment is defined as any subject with study drug duration of 52 days or greater for Arm A and 77 days or greater for Arm B. If the last available post-treatment value is \geq LLOQ, then the subject will be considered a relapse (i.e., will not require confirmation).

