2. Relapse (defined according to the **Relapse₁₂** definition for subjects who complete treatment);
3. Prematurely discontinued study drug with no on-treatment virologic failure (defined as any SVR₁₂ non-responder who prematurely discontinued study drug [study drug duration < 52 days for subjects in Arm A, and < 77 days for subjects in Arm B] and did not meet the **On-treatment virologic failure** definition);
4. HCV reinfection (see definition described earlier);
5. Missing follow-up data in the SVR₁₂ window (defined as any subject who completed study drug without data in the SVR₁₂ window after applying the imputation rules and not meeting the definitions of [1], [2], [3], or [4]);
6. Other (defined as any SVR₁₂ non-responder not meeting the definitions of [1] – [5]).

Reasons for SVR₂₄ Non-Response

Subjects who do not achieve SVR₂₄ (SVR₂₄ non-responders) will be categorized as having:

1. On-treatment virologic failure (see **On-treatment virologic failure definition**);
2. Relapse (defined according to the **Relapse₁₂** definition for subjects who complete treatment);
3. Relapsed after achieving SVR₁₂ (see **Relapse₂₄** definition);
4. Prematurely discontinued study drug with no on-treatment virologic failure (defined as any SVR₂₄ non-responder who prematurely discontinued study drug [study drug duration < 52 days for subjects in Arm A, and < 77 days for subjects in Arm B] and did not meet the **On-treatment virologic failure, Relapse₁₂, or Relapse₂₄** definitions);
5. HCV reinfection;

6. Missing follow-up data in the SVR₂₄ window (defined as any subject who completed study drug without data in the SVR₂₄ window after applying the imputation rules and not meeting the definitions of [1], [2], [3], [4], or [5]);
7. Other (defined as any SVR₂₄ non-responder not meeting the definitions of [1] – [6]).

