10.6.1 Imputation Approaches

In addition to imputing SVR₁₂ as described in Section 6.3, SVR₁₂ rates will be calculated using the following other methods to impute missing HCV RNA values:

- imputing any missing HCV RNA values in the SVR₁₂ window by carrying forward the last non-missing (post-baseline) HCV RNA value prior to the SVR₁₂ window;
- impute as described in Section 6.3 but treat SVR₁₂ non-responders who were categorized as "prematurely discontinued study drug with no on-treatment virologic failure" or "missing follow-up data in the SVR₁₂ window" as successes.

For each of these, the percentage of subjects with SVR₁₂ in each arm and the difference between arms will be presented along with two-sided 95% confidence intervals. The same sensitivity analyses will be performed for SVR₄ in the interim analysis.

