10.8 Additional Efficacy Analyses

The following additional efficacy endpoints will be summarized and analyzed for each treatment arm:

- The percentage of subjects with HCV RNA < LLOQ at each post-baseline visit in the Treatment Period (using data as observed);
- The percentage of subjects with SVR₂₄;
- The percentage of subjects with SVR₄ in Arm B;
- The reasons for not achieving SVR₁₂ and the reasons for not achieving SVR₂₄
- The percentage of subjects with virologic failure through Post-Treatment Week 4 (i.e., the SVR₄ non-responders due to on-treatment virologic failure or Relapse₄).
- The percentage of subjects with virologic failure through Post-Treatment Week 12 (i.e., the SVR₁₂ non-responders due to on-treatment virologic failure or Relapse₁₂).

In the above analyses for SVR and relapse, the percentage of subjects in each treatment arm with a two-sided 95% Wilson score interval and the (unadjusted) difference in rates (Arm A minus Arm B) with a two-sided 95% Wilson score interval will be summarized. Imputations for missing data will be performed as described in Section 6.3 for analyses of SVR and virologic failure, where a missing response will be imputed as a failure after performing the described imputation. All other endpoints will be presented using data as observed.

A summary of the subjects who completed treatment and relapsed (defined as **Relapse_{overall}**) will be prepared displaying the number of subjects relapsing overall and by SVR visit window (within the SVR₄, SVR₁₂, SVR₂₄ windows or after SVR₂₄ window), including the subject numbers and the SVR visit window corresponding to the first occurrence of relapse. A similar summary and listing will be prepared for subjects who prematurely discontinued treatment and relapsed after having HCV RNA < LLOQ at their Final Treatment Visit.

The number and percentage of subjects who do not achieve SVR₁₂ will be summarized by reason for non-response (as defined in Section 10.1). A listing of subject numbers and reason for non-response will be prepared. A similar summary and listing will be prepared for subjects who do not achieve SVR₄ and SVR₂₄.

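### The optimistic SVR12 sensitivity analysis in SAP Section 10.6.1 counts some subjects with measured post-treatment viremia as successes

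*SAP*

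**What the plan says.** Section 10.6.1 states the purpose of its methods: "SVR₁₂ rates will be calculated using the following other methods to impute missing HCV RNA values". The first method carries forward the last post-baseline value before the SVR12 window. The second is to "impute as described in Section 6.3 but treat SVR₁₂ non-responders who were categorized as" either of two reasons for non-response, premature discontinuation without on-treatment virologic failure or missing follow-up in the window, as successes. Both methods are repeated for SVR4 at the interim analysis.

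Section 10.1 defines the categories:

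- **Premature discontinuation (reason 3):** "defined as any SVR₁₂ non-responder who prematurely discontinued study drug [study drug duration < 52 days for subjects in Arm A", or under 77 days in Arm B, without meeting on-treatment virologic failure.
- **Relapse12:** only for subjects below LLOQ at the Final Treatment Visit who completed treatment, where "completion of treatment is defined as any subject with study drug duration of 52 days or greater for Arm A" and 77 days or more for Arm B.
- **EOT failure:** the "value must be collected on or after Study Drug Day 36 and study drug duration" must be at least 36 days.
- **Missing follow-up (reason 5):** completers with no value in the window who do not meet reasons 1 to 4.

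Section 10.8 plans a summary and listing of "subjects who prematurely discontinued treatment and relapsed after having HCV RNA < LLOQ at their Final Treatment Visit". Section 10.9 describes a non-PVF group that includes subjects treated for under 6 weeks who did not suppress.

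Section 5.1.2 forms mITT-GT-VF by "excluding subjects who did not achieve SVR₁₂ for reasons other than virologic failure".

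**The concern.** A missing-data sensitivity analysis should replace only outcomes that were not observed. Reason 3 is defined by treatment duration and the absence of on-treatment failure, not by missing data. A subject can have a measured failure, be categorized under reason 3, and then be counted as a responder. Section 10.9 could list the same subject as viremic and have the sample sequenced.

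What is at stake is the meaning of the optimistic bound on a comparison that rests on very few failures. The SVR4 version matters too, because Section 4.5 says the interim analysis supports regulatory submission in Japan.

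**Working it through.** **1. Tracing the definitions**

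Two kinds of subject stop early and have an observed failure.

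| Subject | Breakthrough or EOT failure? | Relapse12? | Category | Under 10.6.1, method 2 |
|---|---|---|---|---|
| Stops before 52 d (A) or 77 d (B), below LLOQ at Final Treatment Visit, later measured at or above LLOQ, not reinfected | No | No, not a completer | Reason 3 | Success |
| Stops before 36 d, or has no sample from Day 36, never suppressed, no breakthrough | No | No | Reason 3 | Success |
| Stops early after at least 36 d, at or above LLOQ at end of treatment on or after Day 36 | EOT failure | n/a | Reason 1 | Failure |
| Completer, below LLOQ at Final Treatment Visit, then relapses | No | Yes | Reason 2 | Failure |

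The first two rows are the fault. Sections 10.8 and 10.9 show that the SAP expects both kinds. The missing follow-up category does not have this problem, because it excludes subjects who meet reasons 1 to 4.

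**2. Planning figures (SAP Section 4.3)**

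Inputs: 80 and 40 subjects, SVR12 of 96% and 95%, margin -10%, two-sided 95% interval. Exact binomial enumeration of the planned rule (normal-approximation interval, Wilson when both arms are 100%) gives 87.6% power, which agrees with the stated figure of more than 80%. The unpooled closed-form approximation gives 76.8%. Power does not bear further on this point.

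Expected non-responders: 80 × 0.04 + 40 × 0.05 = 3.2 + 2.0 = 5.2.

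Shift per recoded subject: 1/80 = 1.25 points in Arm A, 1/40 = 2.5 points in Arm B.

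**3. Effect on the lower bound**

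The SAP does not say how many viremic early stoppers to expect, so one in Arm A is assumed, with Arm B at 38/40. Section 10.6.1 names no interval, so both types used elsewhere in the SAP are shown.

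Normal approximation: lower bound = d - 1.96 × √[pA(1-pA)/nA + pB(1-pB)/nB].

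- 74/80 v 38/40: d = 0.925 - 0.950 = -2.50 points; SE = √(0.925 × 0.075/80 + 0.95 × 0.05/40) = 4.53 points; bound = -2.50 - 1.96 × 4.53 = -11.38.
- 75/80 v 38/40: d = -1.25; SE = 4.38; bound = -9.84.

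| Arm A | Handling of one viremic early stopper | Normal approximation | Wilson score (Newcombe) |
|---|---|---|---|
| 74/80 | kept as failure | -11.4% | -11.2% |
| 75/80 | recoded as success | -9.8% | -9.6% |
| 74/79 | dropped (mITT-GT-VF) | -9.96% | -9.8% |
| 77/80 | kept as failure | -6.7% | -6.4% |
| 78/80 | recoded as success | -5.1% | -4.6% |

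One subject crosses the margin when Arm A is at 74/80 (92.5%). At 77/80, about the planned rate, one subject does not.

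**4. mITT-GT-VF**

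Section 5.1.2 does not define virologic failure. Section 10.8 describes virologic failure through Post-Treatment Week 12 as on-treatment virologic failure or Relapse12. If that meaning carries over, subjects in the first two rows of the first table leave the population. Section 10.6 uses mITT-GT-VF for sensitivity analyses, Section 10.7 for the stepwise logistic regression, and Section 10.9 for the effect of baseline variants.

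**The case against.** The case against giving this much weight is fair in several respects.

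- **No decision rests on it.** Non-inferiority is judged on SVR12 in the ITT population, where these subjects count as failures, and Section 10.6.1 attaches no margin test to its results. This stands: the primary result is unaffected.
- **Other checks survive.** A reader might infer that the plan has no valid check on missing data. It does. The carry-forward method keeps an observed in-window value and carries a viremic last value forward as viremic, so it does not convert these subjects and needs no change on this account. The listings in Sections 10.8 and 10.9 also keep them visible.
- **Reversal depends on the scenario.** A reader might expect recoding two Arm B subjects to overturn the conclusion, for example 76/80 against 40/40 instead of 38/40. The bound is then -12.2% by Newcombe but -9.8% by the normal approximation, so no general reversal can be claimed. That direction also works against Arm A. The Arm A case above crosses the margin under both intervals, but only at a rate below plan.
- **Not every unsuppressed subject is affected.** Those who meet EOT failure or breakthrough are already virologic failures, including a single breakthrough value followed by loss to follow-up.
- **Restricting relapse to completers is a consistent choice.** It separates failure of a full course from failure after a shortened one. That defends the Relapse12 definition. It does not justify counting a measured failure as a cure under a missing-data method.
- **The mITT-GT-VF part is an inference.** It depends on borrowing the Section 10.8 meaning, because Section 5.1.2 gives none.

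**Conclusion.** The point holds for the second method in Section 10.6.1 and its SVR4 version. As written, it counts as responders early stoppers with observed post-treatment viremia, and some early stoppers who never suppressed. For mITT-GT-VF the same loss of failures follows only if virologic failure there has its Section 10.8 meaning.

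The size is 1.25 points per subject in Arm A or 2.5 in Arm B, against about 5.2 expected non-responders. One Arm A subject can move the sensitivity result across the margin at 74/80 v 38/40, but not at 77/80. The number of such subjects is assumed. The direction of any net bias between arms depends on which arm has more of them, which the SAP does not say. The point is worth correcting, but it does not threaten the primary analysis.

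**What to change.** **Section 10.6.1, second method.** Recode as success only subjects in the two named categories who meet all three conditions: the SVR12-window value is still missing after the Section 6.3 imputation, no HCV RNA at or above LLOQ was measured after the last dose, and the last available value is below LLOQ. Keep observed post-treatment viremia as failure. Apply the same rule to SVR4 with its own window.

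**Section 5.1.2, mITT-GT-VF.** Define virologic failure explicitly for this population. Keep in it, as failures, non-responders with post-treatment HCV RNA at or above LLOQ that is confirmed or is the last available value, whatever the treatment duration, unless they are reinfections. State that this is wider than the Section 10.8 endpoint so that the two are not confused.

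**Cost.** A few sentences and one derivation flag. The primary endpoint, sample size and data collection do not change. The sensitivity estimates become slightly less favourable.

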10.6.2 Assessment of Homogeneity Across Stratification Variables

Heterogeneity across the randomization stratification variable will be examined for the primary efficacy endpoint of SVR₁₂ using the chi-square test of homogeneity. The four strata for the ITT population are:

1. IFN-Naïve, Screening HCV RNA < 6 million IU/mL;
2. IFN-Naïve, Screening HCV RNA ≥ 6 million IU/mL;
3. IFN-Exp, Screening HCV RNA < 6 million IU/mL;
4. IFN-Exp, Screening HCV RNA ≥ 6 million IU/mL.

The proportion of subjects in each treatment arm with SVR₁₂ will be calculated across strata using stratum weighted proportions.

p_s = the proportion of subjects with SVR₁₂ among N subjects, which can be defined as:

$$p_s = \sum_{h=1}^H W_h p_h$$

where N represents the number of subjects in each arm within the ITT population, p_h = the proportion of subjects achieving SVR₁₂ in stratum h , N_h represents the number of subjects in stratum h , $W_h = N_h/N$, and $N = \sum_{h=1}^H N_h$.

Accompanying confidence intervals based on stratum-weighted variances will be calculated using the equations below. The variance of p_s will be estimated by:

$$Var(p_s) = \sum_{h=1}^H W_h^2 \frac{p_h(1-p_h)}{N_h - 1}$$

and the 2-sided 95% confidence interval will be calculated as $p_s \pm z \cdot \sqrt{Var(p_s)}$ where z is the 1- $\alpha/2$ point of the standard normal distribution.

In addition, the number and percentage (p_h) of subjects achieving SVR₁₂ within each of the four strata will be presented.

The difference in SVR₁₂ rates between Arm A and Arm B in h th stratum will be calculated as $d_h = p_{1h} - p_{2h}$. The variances for the difference in proportions, d_h , within the h th stratum will be calculated using the simple asymptotic methods, $Var(d_h) =$

$p_h^*q_h^*(1/n_{1h} + 1/n_{2h})$ where $p_h^* = (n_{1h}p_{1h} + n_{2h}p_{2h})/(n_{1h} + n_{2h})$ and $q_h^* = 1 - p_h^*$, and the 2-sided 95% confidence interval will be calculated as $d_h \pm z\sqrt{Var(d_h)}$, where z is the $1 - \alpha/2$ point of the standard normal distribution. The differences in SVR₁₂ rates and accompanying CI will be presented for each strata.

Differences in proportions between Arm A and Arm B across strata will be calculated based on stratum-adjusted Mantel-Haenszel (MH) proportions, where the difference in the proportions is calculated as $d = \sum_{h=1}^H w_h d_h / \sum_{h=1}^H w_h$ where $d_h = p_{1h} - p_{2h}$ is the difference in the proportions between Arm A and Arm B in hth stratum and $w_h = (n_{1h}n_{2h})/(n_{1h} + n_{2h})$ is the weight for hth stratum. Its continuity corrected variance will be estimated by:

$$Var(d) = \frac{\sum_{h=1}^H w_h^2 \left(\frac{p_{1h}^*(1 - p_{1h}^*)}{n_{1h} - 1} + \frac{p_{2h}^*(1 - p_{2h}^*)}{n_{2h} - 1} \right)}{(\sum_{h=1}^H w_h)^2}$$

Where $p_{1h}^* = (m_{1h} + 0.5)/(n_{1h} + 1)$ and $p_{2h}^* = (m_{2h} + 0.5)/(n_{2h} + 1)$ with $m_{1h} = n_{1h}p_{1h}$ and $m_{2h} = n_{2h}p_{2h}$. So the 2-sided 95% confidence interval will be calculated as $d \pm z\sqrt{Var(d)}$ where z is the $1 - \alpha/2$ point of the standard normal distribution.

The same assessment of heterogeneity across strata will be performed for SVR₄ in the interim analysis.

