4.2 Design Diagram

This is a Phase 3, randomized, open-label, active-control, multicenter study to evaluate the efficacy, safety and pharmacokinetics of ABT-493/ABT-530 in chronic HCV GT2-infected HCV DAA treatment-naïve Japanese adult subjects without cirrhosis. This study consists of a Treatment Period (TP) and a Post-Treatment (PT) Period.

Figure 1. Study Schematic

Approximately 120 HCV GT2-infected DAA treatment-naïve subjects (including subjects who are IFN treatment experienced with or without RBV) without cirrhosis will be enrolled into one of two treatment arms (80 subjects into Arm A and 40 subjects into Arm B)

- Arm A: ABT-493/ABT-530 300 mg/120 mg QD for 8 weeks;
- Arm B: SOF 400 mg QD plus RBV (600 – 1000 mg based on weight divided BID) for 12 weeks.

Subjects meeting all eligibility criteria will be randomized to Arms A or B. The randomization will be stratified by prior IFN-experience (naïve versus experienced) and screening HCV RNA viral load (< or ≥ 6 million IU/mL). Subjects will be randomized in a 2:1 ratio to Arms A (80 subjects) or B (40 subjects).

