4.3 Sample Size

It is planned to enroll a total of 120 subjects in this study. The primary efficacy endpoint of SVR₁₂ will be assessed between treatment Arms A and B.

For the primary endpoint, with 80 subjects in the ABT-493/ABT-530 8-week arm (Arm A) and 40 subjects in the SOF plus RBV 12 week arm (Arm B) and assuming that 96% of the subjects in Arm A achieve SVR₁₂ and 95% of subjects in Arm B (Table 1) achieve SVR₁₂, this study has > 80% power to demonstrate non-inferiority of the ABT-493/ABT-530 8-week treatment arm compared to the active control in SVR₁₂ rate (i.e., a two-sided 95% lower confidence bound for the difference above the non-inferiority margin of –10%). The 10% margin is considered to be an appropriate potential loss of efficacy given the possibility that the current regimen may provide additional clinical advantage over the comparator regimen by shortening the duration of treatment to 8 weeks and eliminating the need for RBV.

Table 1. SVR₁₂ Rates in GT2-Infected Non-Cirrhotic Subjects

| Trial | SVR (n/N) | SVR (%) |
|-----------------------------|------------------|------------------------|
| FISSION ¹ | 59/61 | 97% |
| POSITRON ¹ | 85/92 | 92% |
| FUSION ¹ | 26/29 | 90% |
| VALENCE ¹ | 59/63 | 94% |
| Japanese Study ² | 132/136 | 97% |
| Total | 361/381 | 95%^a |

a. The SVR rate is an unweighted average across the studies.

Note: Data included in the table is for 12-week SOF plus RBV regimen across multiple clinical trials in GT2-infected non-cirrhotic subjects.

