10.6 Sensitivity Analyses for SVR

The following analysis approaches will be used as sensitivity analyses for evaluating SVR₁₂ rates within and between treatment arms for the primary efficacy endpoint:

- A two-sided 95% confidence interval for the SVR₁₂ rates within each arm will be calculated using a Wilson score interval.
- The percentage of subjects achieving SVR₁₂ will be compared using a logistic regression model with treatment arm as a factor, and baseline log₁₀ HCV RNA level, HCV genotype 2 subtype, and prior HCV treatment history as covariates.

- The difference in SVR₁₂ rates (Arm A minus Arm B) will be analyzed using a stratum-adjusted Mantel-Haenszel (MH) proportion with a continuity correction for variance, adjusting for both of the randomization stratum (described in Section 5.2).
- A two-sided 95% confidence interval for the difference in SVR₁₂ rates (Arm A minus Arm B) will be calculated using a Wilson score interval.

The above analyses will be performed on the ITT, and mITT-GT-VF populations, as applicable. The same sensitivity analyses will be performed for SVR₄ in the interim analysis.

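### SAP 10.6.2: the continuity-corrected Mantel-Haenszel interval is far too wide at SVR rates near 100% and fails when a cell holds one subject, and the per-stratum interval uses a null-hypothesis variance

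*SAP*

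**What the plan says.** SAP 4.2 sets the design: "The randomization will be stratified by prior IFN-experience" and by screening viral load, which gives four strata, with 80 subjects in Arm A and 40 in Arm B. The primary analysis (SAP 10.3) is an unstratified normal-approximation interval for the difference, compared with −10%. SAP 10.6 lists, among the sensitivity analyses for the primary endpoint, a "stratum-adjusted Mantel-Haenszel (MH) proportion with a continuity correction for variance".

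SAP 10.6.2 supplies the formulas.

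- **Adjusted difference.** Stratum differences are combined with weights w = n1·n2/(n1 + n2). "Its continuity corrected variance will be estimated by" a sum over strata of w²·[p1*(1 − p1*)/(n1 − 1) + p2*(1 − p2*)/(n2 − 1)], divided by (Σw)², with p* = (m + 0.5)/(n + 1).
- **Difference within a stratum.** The variance for each "stratum will be calculated using the simple asymptotic methods", written out as the pooled form p*q*(1/n1 + 1/n2), with p* here the response rate of both arms combined.

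No rule covers an arm with one subject in a stratum, or a stratum in which everyone responds. The same assessment is repeated for SVR4 at the interim.

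**The concern.** The 0.5 is added separately in each of eight arm-by-stratum cells. When nearly everyone responds, the true binomial variance in each cell is close to zero, so the added half-failure can dominate the estimate. The n − 1 divisor is zero for a cell of one subject, which is possible when 40 Arm B subjects are spread over four strata. A pooled variance belongs to a test of no difference, not to an interval around an observed difference.

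The stratified sensitivity result could therefore appear to contradict a sound non-inferiority result, or fail to compute, because of its formula and not because of the data. The per-stratum intervals would also be reported with the wrong width.

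**Working it through.** **Inputs.** From the SAP: 80 vs 40, margin −10% and two-sided 95% (4.2, 10.3); "assuming that 96% of the subjects in Arm A achieve SVR₁₂ and 95% of subjects in Arm B" (4.3). The SAP gives no stratum sizes, so these are assumed. Layout U has Arm A 46/18/12/4 and Arm B 23/9/6/2. Layout E has 20 vs 10 in every stratum.

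**The plan's own figure.** SAP 4.3 says "this study has > 80% power to demonstrate non-inferiority". Exact enumeration of the primary rule at 96%/95% gives 87.6%, and a Newcombe interval on the crude rates gives 82.4%. The statement reproduces.

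**Where the width comes from.** Take a stratum with 2n vs n subjects, all responders.
- w = 2n/3, and each p*(1 − p*)/(n − 1) is roughly 0.5/n² for that arm's own size.
- The stratum's numerator is about (4n²/9) × 0.5 × (1/(4n²) + 1/n²) = 0.278, whatever n is.
- With Σw = 80 × 40/120 = 26.67, so (Σw)² = 711.1, each stratum adds about 0.278/711.1 = 0.00039.
- The printed formula gives 0.00038, 0.00038, 0.00037 and 0.00042 in layout U, and 0.00038 four times in layout E.

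The inflation therefore grows with the number of strata, not with their sparseness. With 100% response in both arms, layout U gives a variance of 0.00156, SE 0.0395 and lower bound −7.7%. Newcombe on the crude rates gives −4.6%.

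**Worked example, 77/80 vs 39/40, layout U, all failures in the largest stratum.**
- Difference: 0.9625 − 0.9750 = −0.0125.
- Variance: 0.001387 + 0.000377 + 0.000374 + 0.000422 = 0.002560; SE 0.0506.
- Lower bound: −0.0125 − 1.96 × 0.0506 = −11.2%.
- Over all placements of the failures, the bound runs from −9.9% to −11.2%. The primary interval gives −7.6% and the crude Newcombe interval −8.3%.

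**Repeated trials at 96%/95%** (simulation, equal rates across strata).

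| Rule | P(lower bound > −10%) |
|---|---|
| MH as printed, U or E | about 56% |
| MH, n − 1 divisor, no 0.5 | about 85–86% |
| MH with Sato-type variance (other 2:1 layouts and E) | about 87% |
| Primary rule (10.3) | about 88% |

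Coverage of the printed interval is about 99.5% in layout U and 99.2% in layout E. About 31% of trials pass the primary rule and miss −10% here. In a similar layout (44/22/10/4 vs 22/11/5/2) at 85% vs 95%, its one-sided type I error is 0.7%; the Sato-type variance gives 2.2–2.4% across the layouts tried. With two strata the printed rule clears −10% in 73% of trials, and with one stratum in 76%.

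**One subject in a cell.** At n = 1, p* is 0.25 or 0.75, so p*(1 − p*) = 0.1875 is divided by zero. With Arm B 24/10/5/1 the variance is infinite even if everyone responds. Assuming blocks of 3, the chance of exactly one Arm B subject is about 54% if the stratum is expected to hold 3.6 of 120 subjects, 26% at 6, and under 1% at 12.

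**Per-stratum interval.** In both examples below the pooled rate is 28/30, so the pooled SE is √(0.9333 × 0.0667 × (1/20 + 1/10)) = 0.0966.
- 20/20 vs 8/10: unpooled SE √(0.8 × 0.2/10) = 0.1265; ratio 0.76, so 24% too small.
- 18/20 vs 10/10: unpooled SE √(0.9 × 0.1/20) = 0.0671; ratio 1.44, so 44% too large.
- Both arms at 100%: the pooled variance is 0, so the interval has zero width.

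**The case against.** The strongest reply is that nothing confirmatory rests on these formulas. SAP 10.3 alone decides non-inferiority, the error in the adjusted interval is conservative, and SAP 10.6 also lists an unstratified Wilson interval for the difference. The per-stratum intervals are descriptive. All of this stands, and it limits the consequence to reported sensitivity results.

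A reader might also infer several stronger points that the SAP does not support.

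- *That this is the only analysis that accounts for the stratification factors.* The logistic regression in 10.6 includes prior treatment history and baseline log10 HCV RNA, although not as the randomisation strata.
- *That sparse strata cause the inflation.* Four equal strata of 20 vs 10 lose as much. A pooling rule alone would not cure it.
- *That the correction overwhelms the margin in general.* For 77/80 vs 38/40, close to the planned rates, no placement of failures reaches −10% in layouts U or E (worst −9.6%); nor do two arms at 100%.
- *That the stratum-weighted arm rate is an error.* With "where N represents the number of subjects in each arm within the ITT population", Σ(N_h/N)(m_h/N_h) = m/N, the crude rate. It is redundant, but no wrong number results.
- *That the primary interval must be stratified.* An unstratified interval is a prespecified, workable choice, and its stated power reproduces.

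An empty cell is less serious than a cell of one. The Mantel-Haenszel weight is then zero, and dropping the stratum is the natural reading, although the SAP does not say so.

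**Conclusion.** The point holds for two formulas in SAP 10.6.2. The adjusted interval as printed is much too wide at these response rates: about 56% of trials clear −10%, against 82% to 88% for the crude Newcombe and primary rules. About three trials in ten would show a pass on the primary analysis beside a miss on the stratified one. It is not computable when a cell holds one subject. The per-stratum interval has the wrong width in either direction and collapses to zero when everyone responds.

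These figures rest on assumed 2:1 stratum layouts and equal rates across strata. The 56% barely moves between the layouts tried, whereas the chance of a one-subject cell depends strongly on stratum size. The primary conclusion is not affected. The formulas should be corrected before the SVR4 interim, where they are first used and which supports the submission in Japan.

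**What to change.** In SAP 10.6.2:

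1. Keep the Mantel-Haenszel point estimate and weights. Replace the variance with a stratified Newcombe or Miettinen-Nurminen interval, or with a sparse-data (Sato-type) Mantel-Haenszel variance. The Sato-type variance is zero when both arms are at 100%, so it needs the same Wilson fallback that 10.3 already has. Amend the matching bullet in 10.6.
2. State a rule for pooling strata when an arm has fewer than two subjects in a stratum, including which strata are combined. This also protects the variance of the stratum-weighted rate, which has the same n − 1 divisor.
3. Use the Wilson-based (Newcombe) interval for per-stratum differences, as 10.7 already does for subgroups.

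Leave 10.3 unchanged. The cost is a short SAP edit and minor reprogramming. The fix needs no new data and does not change the confirmatory test.
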